## 5. METHODOLOGY

### 5.1 Study objectives

There are two primary objectives, one secondary objective, and six ancillary objectives for this study. The primary safety objective compares the rate of safety composite events between subjects randomized to receive both pulmonary vein isolation and renal artery denervation within one procedure compared to subjects randomized to receive pulmonary vein isolation alone. The primary effectiveness objective compares the proportion of subjects in each study arm that are free from a chronic treatment failure through all follow-up. Further details about study objectives can be found in Section 12.

### 5.2 Subject selection criteria

Subjects will be screened to ensure they meet all the inclusion and none of the exclusion criteria. IRB/MEC and Medtronic approval of the Symplicity AF CIP and Informed Consent Form must be obtained prior to enrolling subjects in the study.

Enrollment of the subject must occur prior to any study procedures take place.

#### 5.2.1 *Inclusion criteria*

- Drug refractory recurrent symptomatic paroxysmal or persistent atrial fibrillation
  - Drug refractory is defined as: failed (drug is ineffective, or patient is intolerant) at least one Class I or III anti-arrhythmic drug
  - If the subject has persistent atrial fibrillation it must have been diagnosed within the last two years from the date of consent with a left atrial volume index  $\leq 40 \text{ ml/m}^2$  within the last year from the date of consent
- Office-based systolic blood pressure  $> 140 \text{ mm Hg}$  based on average of three blood pressure readings despite treatment with 1 or more antihypertensive medication(s). The subject should be on a stable antihypertensive drug regimen with no changes for a minimum of 2 weeks prior to enrollment and the antihypertensive drug regimen is not expected to change for at least 6 months, as determined by the subject's referring cardiologist and/or the investigator.
- Age 18 years to 80 years old
- Willing to give informed consent and agree to all study procedures, and is competent and willing to provide written, informed consent to participate in this clinical study
- Willing and able to be remotely monitored through the Medtronic CareLink® Network

### 5.2.2 Exclusion criteria

- Active systemic infection
- Cryoglobulinemia
- One or more pulmonary vein stents
- Type I Diabetes
- NYHA Class IV heart failure with in the past 6 months
- Renal artery anatomy that is ineligible for treatment including:
  - Lacks at least one renal artery for each kidney with  $\geq 3$  mm and  $\leq 8$  mm diameter and minimum treatable length per the Spyral Instructions for Use prior to a significant arterial branch (*NOTE: All renal arteries with  $\geq 3$  mm and  $\leq 8$  mm diameter with minimum treatable length per the Spyral Instructions for Use shall be treated, including dual renal arteries meeting these morphologic criteria.*)
  - Renal artery stenosis ( $>50\%$ ) or renal artery aneurysm in either renal artery
  - A history of prior renal artery intervention including balloon angioplasty or stenting
  - Renal artery which contain calcification which does not allow at least four radio frequency ablations to be delivered
  - Diffuse fibromuscular dysplasia (FMD) or FMD which does not allow at least four radio frequency ablations to be delivered; FMD defined as visible beading of the artery on angiography
  - Unilateral kidney
- Estimated Glomerular Filtration Rate (eGFR) of  $<30$  mL/min/1.73m^2
- Primary pulmonary hypertension
- Pheochromocytoma, Cushing's Disease, coarctation of the aorta, untreated hyperthyroidism, primary hyperparathyroidism or hyperaldosteronism (Note: treated hyperthyroidism is permissible)
- Myocardial infarction, unstable angina pectoris, syncope, PCI/PTCA, or coronary artery stenting within 3 months prior to signing the consent form, or has widespread atherosclerosis with documented intravascular thrombosis or unstable plaques
- Cerebrovascular accident or TIA within 1 month prior to signing the consent form
- Prior ablation for atrial fibrillation in the left atrium
- Presence of a permanent pacemaker, biventricular pacemaker, atrial defibrillator or any type of implantable cardiac defibrillator (with or without biventricular pacing function)
- Cardiac valve stenosis for which a significant reduction of blood pressure is contraindicated
- A condition that would prohibit or interfere with ability to obtain an accurate blood pressure measurement using the protocol-specified automatic blood pressure monitor (e.g., arm diameter too large for the cuff)
- Serious medical condition, which may adversely affect the safety and/or effectiveness of the participant or the trial (e.g., patients with clinically significant peripheral vascular disease, abdominal aortic aneurysm, bleeding disorders such as thrombocytopenia, hemophilia, or significant anemia)

- Pregnant, nursing or planning to be pregnant. [Female participants of childbearing potential must have a negative serum or urine human chorionic gonadotropin (hCG) pregnancy test prior to angiography]
- Known history of drug use or alcohol dependency, lacks the ability to comprehend or follow instructions, or would be unlikely or unable to comply with study follow-up requirements
- Previous organ transplant
- Currently enrolled or plans to participate in a potentially confounding drug or device trial during the course of this study. Co-enrollment in concurrent studies is allowed when documented pre-approval is obtained from the Medtronic study manager.

### 5.3 Minimization of bias

Selection of subjects, treatment of subjects, and evaluation of study data are potential sources of bias. Methods incorporated in the study design to minimize potential bias include (but are not limited to):

- Subjects will undergo a rigorous screening to confirm eligibility for enrollment with defined inclusion/exclusion criteria prior to enrollment
- All centers will use the same version of the CIP and Case Report Form (CRFs)
- Data collection requirements and study procedures will be standardized for all centers
  - All investigational center personnel and Medtronic personnel will be trained on their respective aspects of the study using standardized training materials
  - All investigational center personnel will be trained on and required to follow the CIP
  - An independent CEC will be utilized to regularly review and adjudicate reported adverse events and deaths
  - An independent DMC will be utilized to safeguard the interests of study subjects and monitor the overall conduct of the study.

In summary, potential sources of bias that may be encountered in this clinical study have been considered and minimized by careful study design.

## 6. STUDY PROCEDURES

### 6.1 Investigator/center selection criteria

An Investigator/center may be included in this investigation if they meet the following criteria:

- Principal Investigator is credentialed in catheter ablation and femoral arterial cannulation in a hospital with an interventional vascular specialist who is credentialed in renal artery interventions. The vascular specialist is to be immediately on-call during the renal denervation procedure to assist as needed in renal artery cannulation, catheter manipulation within the renal artery, and managing any vascular adverse events such as renal artery perforation or dissection.

- Principal investigator has experience using the Arctic Front®/ Arctic Front Advance/Arctic Front Advance Pro Cardiac Cryoablation Catheter system in at least 10 cases.
- Center has a Medtronic CryoCath CryoConsole installed at the facility (Generation 5 console).
- Willingness to perform both pulmonary vein isolation ablation with the Arctic Front Advance/Arctic Front Advance Pro Cardiac Cryoablation Catheter system and renal artery denervation with the Symplicity Spyral Catheter and Symplicity G3 Generator during the same case.
- Principal investigator has access to an adequate number of potential subjects.
- Sufficient experienced staff and equipment (e.g. study coordinator, renal duplex ultrasound, renal angiography, and trans-thoracic echocardiogram (TTE)) to execute and maintain protocol compliance.

## 6.2 Center activation

During the activation process (prior to subject enrollment), Medtronic will train center personnel on the CIP, relevant standards and regulations, informed consent, data collection and reporting tools. If new members join the investigational center team, they will receive training on the applicable clinical study requirements relevant to their role before contributing to the clinical study.

Prior to performing study related activities, all local regulatory requirements shall be fulfilled, including, but not limited to the following:

- Medtronic and IRB/MEC approval (and membership roster/voting list, as required by local law) of the current version of the CIP and Informed Consent Form, subject facing materials, Report of Prior Investigation as required by local laws and other materials, as necessary
- Regulatory authority approval or notification (as required per local law)
- Fully executed Clinical Trial Agreement (CTA)
- Investigator Curriculum Vitae (CV)
- Delegation of center personnel responsibilities
- Documentation of study training
- Financial Disclosure

In addition, all participating center staff must be trained on the current version of the CIP and must be delegated by the principal investigator to perform study related activities.

Additional requirements imposed by the IRB/MEC and regulatory authority shall be followed.

Medtronic will provide each study center with written documentation of study center/investigator readiness, this letter must be received prior to subject enrollment. Additional center personnel included after the initial activation will be notified when all requirements have been completed.

## 6.3 Equipment requirements

The following equipment must be available at each center to support study activities:

- Trans-thoracic echocardiogram

- Renal angiography
- Renal duplex ultrasound

The maintenance and calibration of the equipment listed above will be assessed by the participating center following their normal processes. Clinical monitors will not monitor maintenance or calibration schedules.

The sponsor will supply all required study materials for appropriate data collection before study start, like the office blood pressure monitors (OBPs). Medtronic will control the supply of devices and study materials

#### **6.4 Role of the sponsor representative during study procedures and follow up visits**

Sponsor representatives may provide support as required for the study under supervision of the Principal Investigator, including:

- Provide study training relevant and pertinent to the involvement of personnel conducting study activities and investigator responsibilities
- Technical support at the pulmonary vein isolation, renal denervation and Reveal LINQ insertion procedures under the supervision of a study investigator, but no data entry, shall be performed by Medtronic personnel or their representatives at sites
- Monitoring and auditing activities
- Follow up visit activities involving the Reveal LINQ device and CareLink

#### **6.5 Data collection**

Clinical data is collected at designated time points throughout the study. Data will be collected using an electronic data management system for clinical studies.

Data will be stored in a secure, password-protected database which will be backed up nightly. Data will be reviewed using programmed and manual data checks.

Data queries will be made available to study centers for resolution. Study management reports may be generated by Medtronic to monitor data quality and study progress. At the end of the study, the data will be frozen and retained indefinitely by Medtronic. Data collection requirements are summarized in Table 5.

Table 5: Data collection and study procedure requirements at subject visits

	Enrollment/Baseline	CT Scan	Cryoablation Procedure	Renal Artery Denervation	Reveal LINQ Insertion	Hospital Discharge	1 month	6 month	Every 6 months until study end closure	12 month	Unscheduled	Exit	Repeat cryoablation Procedure (0-90 days), if performed
Informed Consent	x												
Inc/Exc criteria	x	x		x								x	
Medical history	x												

[figure not shown]
	Enrollment/Baseline	CT Scan	Cryoablation Procedure	Renal Artery Denervation	Reveal LINQ Insertion	Hospital Discharge	1 month	6 month	Every 6 months until study end closure/12 month	Unscheduled	Exit	Baseline	Cryoablation	Hospital Discharge	Repeat cryoablation Procedure (0-90 days), if performed
Physical exam	x						x	x	x	x	x	x		x	
Trans-Thoracic Echocardiogram	x (1)														
Review medications	x				x	x	x	x	x	x	x	x	x	x	
Office BP x3	x					x (8)	x (8)	x (8)	x		x		x		
Blood and urine labs: Serum Creatinine (sCr), Spot urine albumin and creatinine and Cystatin C	x				x	x	x			x (2)					
Review of symptoms	x						x	x	x	x					
Randomization	x														
Pregnancy test	x (3)														
Transesophageal Echocardiogram (TEE) (3)		x (4)													
Renal angiogram for Treatment group only			x												
Procedure information		x	x	x	x								x		
CareLink in-office interrogation (5)					x (6)		x	x	x	x					
CareLink manual home transmission									x (5)		x				
Renal Artery Imaging-Duplex Ultrasound								x (7)							
Adverse Events, Reveal LINQ System Modification, Death, Study Deviation, Device Deficiencies															As they occur

- For subjects with persistent AF, perform during the 12 month interval preceding the Consent Date, or between Consent Date and Procedure Date.
- Optional, if performed.
- Perform within 5 days prior to the Procedure.
- TEE at baseline to assess for LA thrombus as indicated by the 2012 HRS/EHRA/ECAS Expert Consensus Statement on Catheter and Surgical Ablation of Atrial Fibrillation (Section 6.7).
- CareLink transmissions need to occur at a minimum one time per month. For the monthly CareLink transmissions that coincide with a scheduled follow-up visit (i.e. 1 or 6-month visits), a monthly transmission

is not required but perform an in-office device interrogation and data transfer to Medtronic. A CareLink transmission may be used as a substitute for an in-office device interrogation.

6. Ensure a device interrogation with final programmed settings is transferred to Medtronic. This may be at the time of insertion or prior to hospital discharge.
7. Only for subjects who underwent the renal denervation procedure (randomized to the Treatment group). If clinically significant renal artery stenosis is suspected, a follow-up renal angiogram will be performed.
8. Office blood pressure (according to guidelines in Appendix G), needs to be obtained if an office visit occurs or during alternative methods of data collection as described in section 6.18.1.

Figure 1: Study design flowchart

## 6.6 Patient informed consent process

Patient informed consent is defined as legally effective, documented confirmation of a subject's (or their legally authorized representative or guardian) voluntary agreement to participate in a particular clinical study after information has been given to the subject on all aspects of the clinical study that are relevant to the subject's decision to participate. This process includes obtaining Consent and an Authorization to Use and Disclose Personal Health Information/Research Authorization/other privacy language as required by law that has been approved by the investigational center's IRB/MEC and signed and dated by the subject (or their legally authorized representative, US ONLY). A subject may only consent after information has been given to the subject on all aspects of the clinical investigation that are relevant to the subject's decision to participate.

Prior to enrolling subjects, each investigational center's IRB/MEC will be required to approve the Consent Form, and Authorization to Use and Disclose Personal Health Information/Research Authorization/other privacy language as required by law. The document(s) must be controlled (i.e. versioned and/or dated) to ensure it is clear which version(s) were approved by the IRB/MEC. Any adaptation of the sample Consent Form must be reviewed by Medtronic and the IRB/MEC reviewing the application prior to enrolling subjects. Refer to Appendix D: Informed consent templates for the sample Consent Form.

Prior to initiation of any study-specific procedures, patient informed consent must be obtained from the subject (or their legally authorized representative or guardian). The informed consent process must be conducted by the principal investigator or an authorized designee, and the Consent Form and Authorization to Use and Disclose Personal Health Information/Research Authorization/other privacy language as required by law must be given to the subject (or their legally authorized representative or guardian) in a language he/she is able to read and understand. The process of patient informed consent must not be conducted using coercion or undue improper influence on or inducement of the subject to participate by the investigator or other center personnel.

The process of obtaining patient informed consent shall:

- Not waive or appear to waive subject's legal rights
- Use language that is non-technical and understandable to the subject
- Provide ample time for the subject to read and understand the informed consent form and to ask questions, receive answers and consider participation
- Include a personally dated signature of the subject acknowledging that their participation in the study is voluntary

In Europe, include a personally dated signature by the Principal Investigator or authorized designee responsible for conducting the informed consent process.

If the Consent Form is obtained the same day the subject begins participating in study-related procedures, it must be documented in the subject's case history that consent was obtained prior to participation in any study-related procedures. It is best practice for the informed consent process to be documented in the subject's case history,

regardless of circumstance. It is also best practice to document in the subject's case history if they were re-consented for any reason.

In the event the subject cannot read and/or write, witnessed (impartial third party) patient informed consent will be allowed, provided detailed documentation of the process is recorded in the subject's case history and the witness signs and dates the patient informed consent. In Europe, when a subject cannot read and/or write, an independent witness shall be present throughout the process, the written PIC Form and any other information shall be read aloud and explained to the prospective subject. The subject should "make his mark" (sign or otherwise physically mark the document so as to indicate consent) on the Consent Form as well. The Consent Form should document the method used for communication with the prospective subject and the specific means by which the prospective subject communicated agreement to participate in the study.

The original or a copy of the signed Consent Form must be filed in the hospital/clinical chart and with the subject's study documents.

The Consent Form and Authorization to Use and Disclose Personal Health Information/Research Authorization/other privacy language as required by law must be available for monitoring and auditing. Any Medtronic Field personnel who support study procedures must be able to review the subject's signed and dated Consent Form and verify its completeness prior to proceeding with study procedures. In the event the Medtronic Field personnel identify patient informed consent as being incomplete, the study procedures will not be allowed to occur until the consent of the subject can be adequately and appropriately obtained.

Any changes to a previously approved Informed Consent Form throughout the course of the study must be approved by Medtronic and the IRB/MEC reviewing the application before being used to consent a prospective study subject. The document(s) must be controlled (i.e. versioned and/or dated) to ensure it is clear which version(s) were approved by the IRB/MEC. All important new information should be provided to new and existing subjects throughout the study.

## 6.7 Medications

The collection of the following medications will take place during the course of this study: anticoagulants, those prescribed to treat atrial fibrillation, including those used for rate control, and those prescribed to treat hypertension. Information collected will include the medication name, purpose and start/stop dates.

It is recommended to maintain all randomized subjects on their baseline hypertensive medications without changes until the 6-month visit. A study deviation is not required if changes are made to these medications.

If a subject is on amiodarone, it is recommended to take them off 4-6 weeks before the end of the 90-day post cryoablation procedure blanking period.

It is recommended that subjects be off all antiarrhythmic medications within 90 days post cryoablation procedure.

Medication changes that occur specifically because the subject will undergo the study procedures should not be recorded.

All medications are permitted in this study with the exception of investigational drugs that may confound the study results.

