Case Report Form (CRF) data will be used to determine if subjects have or have not used Class I and III anti-arrhythmic drugs following the blanking period. If a subject has not used Class I anti-arrhythmic drugs and has not used Class III anti-arrhythmic drugs at all following the blanking period, then they will be used for this analysis. If a subject has used either Class I or Class III anti-arrhythmic drugs after the blanking period, then they will be excluded from this analysis.

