7.10.8.5. Datasets Analyzed

The following subjects will be included in this analysis:

- All subjects in the mITT analysis set that do not undergo an additional pulmonary vein ablation procedure during the 90 day blanked follow-up period will be included this analysis

AND

- Have not used Class I and III anti-arrhythmic drugs following the blanking period

Data from the Other Medication Log CRF will be used to determine if subjects have or have not used Class I and III anti-arrhythmic drugs following the blanking period. The log collects medication names which are classified as Class I or Class III anti-arrhythmic, etc. (SAS variable C_NAME). If a subject has not used Class I or III anti-arrhythmic drugs at all following the blanking period, all of their follow-up will be used for this analysis. If a subject has used either Class I or Class III anti-arrhythmic drugs after the blanking period, they will be excluded for this analysis.

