7.10.9.3. Endpoint Definition

The endpoint for this objective is the percent of time a subject is in AF over all of their follow-up after the blanking period.

Data obtained directly from the Reveal LINQ device will be used to calculate this endpoint in the following manner:

- Blanking period: 90 days after the cryoablation procedure
- Numerator: time in AF from Reveal LINQ device after the blanking period
 - Start date: Index cryoablation procedure date + 91
 - End date: End of follow-up time (latest date Reveal LINQ device data was recorded from study device data)
 - Numerator: The total amount of time (e.g., hours, days, etc.) the device shows the subject is in AF starting on the start date and ending on the end date
- Denominator: total follow-up time for a subject after the blanking period
 - Start date: Index cryoablation procedure date + 91
 - End date: End of follow-up time (latest date Reveal LINQ device data was recorded from study device data)
 - Denominator (days): End date – start date
 - Note: The denominator calculation assumes that the device will be monitoring for AF every day from when it is implanted to the latest date Reveal LINQ device data is recorded from the study device data. If it is possible that the device will not record 24 hours a day, 7 days a week, then we may need to use the device data to determine the total follow-up time where the device was monitoring for AF.
- Endpoint: (Numerator/Denominator) x 100

- Ensure time units for numerator and denominator are the same. The choice of denominator units will be made to most sensibly report the results, depending on how much time subjects are in AF (e.g., hours, days, etc.).

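### Protocol 6.7 exempts procedure-driven drug changes from recording, yet the SAP uses the medication log to decide who enters Ancillary #5, so some subjects can be wrongly excluded or included

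*Protocol*

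**What the plan says.** Protocol 6.7 collects anticoagulants, AF drugs (rate control included) and antihypertensives. On content it says: "Information collected will include the medication name, purpose and start/stop dates". On antiarrhythmics it says: "It is recommended that subjects be off all antiarrhythmic medications within 90 days post cryoablation procedure", and it gives a separate recommendation on when to stop amiodarone. The next sentence is the exemption: "Medication changes that occur specifically because the subject will undergo the study procedures should not be recorded". It names no drug class and is not limited to temporary holds.

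SAP 7.10.8.5, on the Ancillary #5 data, says: "Data from the Other Medication Log CRF will be used to determine if subjects have or have not used Class I and III anti-arrhythmic drugs" after blanking. SAP 7.1.3 refers more loosely to CRF data and gives the consequence: "If a subject has used either Class I or Class III anti-arrhythmic drugs after the blanking period, then they will be excluded from this analysis". The period that counts follows from SAP 7.10.9.3: "Blanking period: 90 days after the cryoablation procedure".

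Protocol 6.16, 6.18.1, 6.19 and 6.24 also have medications assessed at discharge, at 1 and 6 months, every 6 months after that, at unscheduled visits and at exit. SAP 7.4 plans no imputation. Neither document says how a log entry without a stop date is to be read.

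**The concern.** The two rules conflict. The SAP needs complete Class I/III start and stop dates to establish each subject's drug status after day 90. The protocol tells sites to leave some of those dates out, for a reason that is likely to apply to antiarrhythmics around an AF ablation. Every subject must have failed at least one Class I or III drug to be eligible (Protocol 5.2.1), so these drugs are directly relevant to the population.

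What is at stake is who belongs in the Ancillary #5 set, and hence the off-drug success estimate, its log-rank test and its hazard ratio. Protocol 12.4.2 says the study is meant to inform the design of a pivotal trial, and off-drug success is a result that a pivotal designer would look at.

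**Working it through.** The plan gives no figure for how often this occurs, so the main check is to follow each kind of unrecorded change through the Ancillary #5 rule.

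**Inputs**
- Recording rule: Protocol 6.7, changes made because of the coming study procedures are not logged.
- Classification rule: SAP 7.1.3 and 7.10.8.5, any Class I/III use after day 90 means exclusion.
- Reading of an open entry: not stated. I assume that a blank stop date is taken as ongoing use.

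**Trace, before any later correction of the log**

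| Unrecorded change to a Class I/III drug | What the log shows | True status after day 90 | Result |
|---|---|---|---|
| (a) Stopped for the ablation, not resumed | Entry still open | Off drug | Wrongly excluded |
| (b) Started for the ablation, ended by day 90 | No entry | Off drug | Correctly included |
| (c) Started for the ablation, continued past day 90 | No entry | On drug | Wrongly included |
| (d) Held and then resumed | Entry still open | Determined by the later record, which the hold does not alter | Correct |

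Two of the four patterns misclassify, in opposite directions. That counts types of change and is not a rate.

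**Scale, for illustration only**

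As a base, take the SAP section 6 design: 70 subjects and a maximum of 41 events. A three-look simulation at 14, 19 and 41 events, with boundaries 2.576, 2.611 and 2.049 and hazard ratio ln(0.75)/ln(0.50) = 0.415, reproduces the SAP's power figures: 17.6% + 10.1% + 50.9% = 78.6%. That power belongs to the primary objective, which does not use drug status, so this point leaves it unchanged.

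For the precision of a hazard ratio with 1:1 arms and d events, the standard error of the log hazard ratio is about 2/√d. The 95% interval is then the estimate divided and multiplied by exp(1.96 × 2/√d). Suppose a fraction m of subjects is wrongly excluded, equally across arms and outcomes, so that d = 41 × (1 − m):

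| m (assumed) | d | Interval factor |
|---|---|---|
| 0 | 41 | exp(3.92/√41) = 1.84 |
| 5% | 38.95, about 39 | 1.87 |
| 10% | 36.9, about 37 | 1.91 |
| 20% | 32.8, about 33 | 1.98 |
| 30% | 28.7, about 29 | 2.08 |

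The loss of precision is modest across this range. The actual starting set is smaller than 70, because subjects with a repeat ablation in the blanking period and true drug users are also removed. The table does not cover pattern (c), which mixes on-drug subjects into an off-drug estimate and is a matter of validity rather than precision.

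**The case against.** The strongest reply concerns scope. The exemption speaks of procedures the subject is going to undergo, which most naturally means changes made before the procedure. The antiarrhythmic withdrawal that the protocol recommends comes afterwards, within the 90 days, and on that reading it would be logged with its date. This stands, and it narrows the problem. It does not remove it: a stop made ahead of the ablation is pattern (a), and a start made ahead of it can become pattern (c). The exemption also follows directly on the two recommendations about stopping antiarrhythmics, so a site could apply it to those stops as well. Neither document settles which reading is meant.

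The second reply is that medications are reviewed repeatedly, and that Protocol 13 requires CRF data to agree with source, with data checks and queries. A drug not taken for six months, or still taken after day 90, would come up at several contacts. This also stands in part: some entries may well be corrected. But no text says that a review overrides the recording exemption.

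Third, reading a blank stop date as ongoing use is an inference. The log and its completion instructions are not in these documents, and that 6.7 feeds the Other Medication Log is itself a reasonable inference. This is why the SAP needs a stated rule for open entries.

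A reader might also infer bias between arms, because blinding ends after pulmonary vein isolation. The documents do not support that for the changes at issue. Under Protocol 6.9, subjects and center personnel are still blinded when changes are made ahead of the procedure. Continuation and log correction come later, without blinding, but nothing in the plan indicates that they would differ by arm.

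**Conclusion.** The conflict is real and its reach is narrow. Followed as written, Protocol 6.7 and SAP 7.10.8.5 can place subjects wrongly in or out of the Ancillary #5 set. That depends on three things: a Class I/III change made because of the procedure, a site applying the exemption to it, and no later correction of the log. Wrong exclusion depends also on an open entry being read as ongoing use.

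Three stronger readings are tempting and unsupported. First, misclassification is possible rather than certain, as the trace shows. Second, nobody moves to the wrong randomized group; the error concerns membership of one analysis set. Third, a count per arm can be produced only from assumed proportions. For example, 30% to 50% on such a drug, with a quarter to a half of those stopping for the ablation, gives 35 × 0.30 × 0.25 = 2.6 to 35 × 0.50 × 0.50 = 8.8 subjects. Neither proportion is in the documents, the sum allows nothing for later correction, and the Ancillary #5 set is smaller than 35 per arm.

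Ancillary #5 has no hypothesis and no performance criteria (SAP 7.10.8.1 and 7.10.8.2), although it carries a log-rank test at 0.05. The primary endpoint does not use drug status. The point is worth correcting because the rules contradict each other and the repair is cheap.

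**What to change.** The changes concern data capture and analysis rules only; treatment is not affected.

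1. Amend Protocol 6.7 so that every start and stop of a Class I or III antiarrhythmic is recorded with its date, whatever the reason. The exemption can remain for other drugs as far as Ancillary #5 is concerned.
2. State in SAP 7.10.8.5 how a Class I/III entry with no stop date is resolved, and use the same data source in SAP 7.1.3.
3. For randomized subjects, query open Class I/III entries against source before database freeze. In the same check, look in source for Class I/III use after day 90 that has no log entry, since querying open entries cannot find pattern (c).

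The third step matters because the Protocol Appendix I change history shows 100 subjects enrolled at version 18, so a rule that applies only to new entries would miss most of them. Protocol 16.1 has the case histories retained, so past dates can be recovered.

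The cost is a few more log lines and queries per subject, one SAP rule and a minor protocol revision. Under Protocol section 4 that revision needs approval from the sponsor, FDA or other regulatory body, and each IRB/MEC. If that is judged too slow, steps 2 and 3 can go ahead first and would recover most of the benefit.
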